Implementation of the DSMS at CDE-UNMH: The CDE-UNMH program uses the DSMS group education approach. Patients attend a six-week group instructional session with nine hours of class plus a one-on-one follow-up with a certified diabetes educator to provide individualized support by creating a customized education plan. The group sessions have discussion supported by didactic conversation "maps" where the facilitator guides but does not control the conversation based on session thematic goals. Patients then complete self-assessment forms. This format is the foundation of the DSMS Model for creating patient empowerment and program cultural competence.

Comparator #2.

The Chronic Care Model (CCM).^{31,44} The One Hope Centro de Vida Health Center Diabetes Program (One Hope) is based on the Chronic Care Model (CCM).^{31,44} The Chronic Care Model Framework: The CCM is "a systematic approach to restructuring medical care to create partnerships between health systems and communities"⁴⁴ by addressing not only the medical but also the cultural and linguistic needs of patients through the inclusion of cultural competence in the delivery system design.³¹ The CCM involves six synergistic domains: 1.) Improved access to care, 2.) Patient self-management support, 3.) Patient decision support, 4.) Care coordination, 5.) Integrated health information systems, and 6.) Access to community resources. The use of the CCM framework has been shown to yield significant results in the treatment of diabetes and is being used widely in chronic disease management.⁴⁵ To create a holistic care regime, the CCM focuses on addressing social determinants of health by meeting the medical, cultural, and linguistic needs of patients through integration of cultural norms and social relationships from the patient population into program design.³¹

Implementation of the CCM at One Hope: The One Hope program is designed to address the specific needs of Latino patients from low-income households^{32,33} by creating comprehensive, integrated, wrap-around services focused on culturally competent care.^{31,44} One Hope emphasizes Spanish as the language for service provision³³ and access to care

PROTOCOL TITLE: Comparing Program Options for Latinos with Diabetes

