regardless of ability to pay. The One Hope facility provides a physical environment that reflects the lifestyle and economic capacity of patients to make them feel comfortable and that they “belong” (in contrast to more clinical, corporate, or academic medical settings). One Hope is a community-run clinic with a director and staff who are members of the community and who are culturally and economically similar to the patients they serve, reducing the hierarchical power relationship that generally exists between patients and providers. This approach is evident in the way that doctors at One Hope share decision-making by engaging the patient and their family members in creating a plan for diabetes self-management.^{46,47} In addition, patients, caregivers and family members participate in a variety of program activities including cooking and nutrition workshops, zumba classes, and citas compartidas sessions (“shared appointments”).^{30,47-49} These shared appointment sessions allow patients, social supports and family members to share their stories and experiences in a peer support setting with facilitation by medically trained providers. But providers also “co-learn” from the patients.^{27,35,36} Through shared decision-making and shared appointments, providers learn about the realities of patients’ lives and their daily struggles at a level that goes beyond the interaction that normally occurs in a clinic. This helps the provider to be culturally competent by understanding diabetes from the perspective of the patient. Sharing experiences with peers and providers and including family members in activities offers a different level of social support for the patient by creating an enhanced feeling of intimacy and inclusion within the program. Innovative salidas (exit interviews), conducted routinely with all patients by a bilingual health navigator ensures that the patient understands and feels capable of implementing a doctor’s instructions, and integrates health system information by allowing the health navigator to communicate details of patient status back to the provider.³²

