Programmatic assessment. We will inventory each program regarding program design, size, structure, operation, and theoretical/philosophical orientation; professional qualifications/training of program providers; activities or resources available through the programs; strategies in place for Spanish language use or acceptance, inclusion of social supports and family, accommodation of challenges created by patients' limited socioeconomic circumstances, and the inclusion of stress management techniques; and data on referrals to the program, sign-ups, participation, no-shows, and attrition. We will conduct up to 36 interviews with key staff and/or providers (6/year x 2 sites x 3 years) to obtain their perspectives on implementation of the programs during the period of the study. Interview questions will be semi-structured to allow participants to contribute to the direction of the interview in relation to issues and ideas that they consider to be most relevant and important. Interviews will be audio-recorded and transcribed. We will assess patient and social support perceptions of the program interface using a cultural competence survey^{88,89} that asks about physician bias, inter-cultural understanding, respectful interactions, language barriers, experiences of discrimination, and issues of trust. Administration of the survey is described in the paragraph immediately below this one. The cultural competence portion of the survey will not be administered at baseline as the participant will not yet have experience with which to rate the program. To gather qualitative information, we will include questions on programmatic interface in interviews and focus groups with patients and social supports that are described two paragraphs below.

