Surveys. We will hire four individuals from the population of study to work as PDCSs. The PDCS at each site will administer a survey orally to all patient and social support participants at baseline (when they enter the study), with follow-up at 3, 6, and 12 months. The survey will consist of questions from or modified from four validated and reliable tools: 1.) The *Consumer Assessment of Healthcare Providers and Systems Cultural Competence Set (CAHPS-CC)*^{88,89} [as part of the programmatic assessment discussed in the preceding paragraph—will be administered at 3, 6 and 12 months only]; 2.) The *Diabetes Knowledge Questionnaire (DKQ)*^{51–53,112}; 3.) The *Patient Activation Measure (PAM-13)*^{55–62,113}; and 4.) The *Patient Health Questionnaire 9 (PHQ-9)*.^{70–73}

Interviews with patient and social support participants. We will conduct 72 interviews with patients and social supports (12/year x 2 sites x 3 years). Following Guest, Bunce and Johnson,¹¹² and [name]'s own experience with interview data, we believe that data sets of 12 interviews per site per year will capture a sufficient range of responses to achieve

PROTOCOL TITLE: Comparing Program Options for Latinos with Diabetes

thematic saturation. Our sampling frame for each set of 12 interviews will include six patients and six social supports. Interviews will be conducted with the social supports who correspond to the six patient interviewees. Interviews will follow the same format described in the programmatic assessment above. Spanish transcripts will be translated into English for analysis.

Focus groups. We will conduct 12 focus groups (2/year x 2 sites x 3 years). Focus group participants will be distinct from those recruited to participate in the interviews described in the preceding paragraph. Focus groups will include six distinct participants each (three patients and their corresponding social supports per focus group x 12 focus groups = 72 participants). The focus group questions and protocol will be an adaptation of that described above for the interviews.

Physical Measures. These measures will be obtained from patients at baseline with follow-up at 3, 6, and 12 months:

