We will create a database with all interview and focus group transcripts. We will conduct a theory-driven qualitative content analysis. We will read through transcripts to identify conceptual categories and patterns related to specified domains of inquiry, create a qualitative codebook, and develop conceptual summaries for each transcript. Following review and summary, we will code transcripts for systematic themes and sub-themes within the domains. We will explore interconnections between theme categories and develop a holistic interpretation of the data.

Statistical Analysis Aim 3. We will conduct analyses to assess successful patient management of their diabetes (Aim #3), our secondary outcomes, by measuring their A1c from blood samples drawn, BMI calculations, cortisol from hair samples, and PHQ-9 scores obtained at baseline, 3, 6, and 12 months. Clinical analysis of blood samples will use A1c tested on whole blood as described previously. Change in A1c over the four time points in each of the diabetes self-management program models will be evaluated by fitting a linear mixed model to A1c with the primary independent variable treatment site while adjusting for demographic covariates, social support and knowledge, the measures hair cortisol indicating stress levels, and participant and social support scores on the CAHPS-CC. An interaction between time and site will be included to explore how A1c scores change over time. For the secondary endpoint analysis, REML-adjusted least-squares mean estimates of change in A1c from baseline to 6 months post-intervention will be reported along with their 98.3% confidence intervals (the significance level includes a Bonferroni adjustment for three secondary outcomes). A model incorporating the 12 month time point will also be evaluated. BMI and depression scores will be analyzed similarly.

11.2 Provide a power analysis.

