program interface using a cultural competence survey that asks about physician bias, inter-cultural understanding, respectful interactions, language barriers, experiences of discrimination, and issues of trust. To gather qualitative information, we will include questions on programmatic interface in interviews and focus groups with patients and social supports.

ii. Surveys. The PDCS at each site will administer a survey to all patient and social support participants at baseline (when they enter the study), with follow-up at 3, 6, and 12 months. The survey will consist of questions from or modified from four validated and reliable tools: 1.) The *Consumer Assessment of Healthcare Providers and Systems Cultural Competence Set* (CAHPS-CC) [as part of the programmatic assessment discussed in the preceding paragraph]; 2.) The *Diabetes Knowledge Questionnaire* (DKQ); 3.) The *Patient Activation Measure* (PAM-13); and 4.) The *Patient Health Questionnaire 9* (PHQ-9). Because the CAHPS-CC is an assessment of program cultural competence and requires participant experience with the program, it will not be administered as part of the baseline survey.

iii. Interviews. We will conduct 72 interviews with patients and social supports. Our sampling frame for each set of 12 interviews will include six patients and six social supports. Interviews will be conducted with the social supports who correspond to the six patient interviewees. Interviews will follow the same format described in the programmatic assessment above. Spanish transcripts will be translated into English for analysis.

iv. Focus groups. We will conduct 12 focus groups. Focus group participants will be distinct from those recruited to participate in the interviews described in the preceding paragraph. Focus groups will include six distinct participants each. The focus group questions and protocol will be an adaptation of that described above for the interviews.

v. Physical Measures. These measures will be obtained from patients at baseline with follow-up at 3, 6, and 12 months:

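### Every social support is scheduled to rate the program on CAHPS-CC at 3, 6 and 12 months, but nothing requires or records that the support has had contact with it, and the likelihood of contact may differ by site

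*Combined protocol and SAP*

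**What the plan says.** **Who is asked, and when.** Section 9.2 (Programmatic assessment) states: "We will assess patient and social support perceptions of the program interface using a cultural competence survey". Section 9.2 (Surveys) sets the schedule: "The PDCS at each site will administer a survey orally to all patient and social support participants at baseline", with follow-up at 3, 6 and 12 months. The CAHPS-CC part "will be administered at 3, 6 and 12 months only".

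**Why not at baseline.** Section 9.2 explains that this part "will not be administered at baseline as the participant will not yet have experience with which to rate the program". Section 11.5 (Surveys) makes the condition explicit: the instrument "requires participant experience with the program, it will not be administered as part of the baseline survey".

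**Who may be a support.** Under Section 3.2 a support is an adult whom the patient names and who agrees to join. No contact with the program is required.

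**What the programs offer supports.** Section 2.2 says of One Hope that "patients, caregivers and family members participate in a variety of program activities"; family are also drawn into planning the patient's self-management. Of CDE-UNMH it says: "Patients attend a six-week group instructional session with nine hours of class plus a one-on-one follow-up with a certified diabetes educator". That description gives supports no role and does not shut them out. Section 9.2 lists each program's inclusion of supports and family among the features still to be inventoried.

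**How the scores are used.** They contribute to the Aim 1 description of each program. In Section 11.1 (Statistical Analysis Aim 3) the A1c mixed model adjusts for "participant and social support scores on the CAHPS-CC", and BMI and depression scores are to be analysed in a similar way.

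**The concern.** The plan sets a condition for a valid rating, namely experience of the program, and applies it only at baseline. From 3 months on, elapsed time stands in for experience. That is a fair proxy for a patient who has entered the program. It is weaker for a support, who may never have met the staff.

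The gap may not be even across sites. If supports commonly join in at One Hope and less often at CDE-UNMH, the share of ratings that are second-hand or blank would track site, which is the comparison variable. Two things follow. A difference in support ratings could be read under Aim 1 as a difference in cultural competence when part of it is a difference in who had anything to rate. In the Aim 3 models, a covariate whose meaning or completeness varies by site could bias the site effect or cost observations.

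**Working it through.** **1. The condition against the schedule.**

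- Condition (Section 11.5): the rater needs experience of the program.
- Schedule (Section 9.2): all patients and all supports, both sites, 3, 6 and 12 months.
- Entry rule for supports (Section 3.2): named by the patient and willing.
- Check on contact: the sections that set up the survey (9.2 and 11.5) give no screening item, skip rule, not-applicable option or exemption for supports.

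The condition is therefore not secured for supports at either site.

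**2. Site by site.** One Hope describes activities for family and caregivers; CDE-UNMH describes activities for patients. This makes lower support contact at CDE-UNMH plausible. It does not establish it, and One Hope supports are not required to attend either.

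**3. Scale.** Section 24.1 plans 120 supports per site. Scheduled support ratings per site: 120 × 3 = 360. With the 20% attrition in Section 11.2, 120 × 0.8 = 96 pairs remain, giving 96 × 3 = 288. The share given without contact cannot be derived from the documents.

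**4. The plan's own A1c power.** Inputs from Section 11.2: n = 96 per site, difference 0.5, SD 1.0, two-sided α = 0.017.

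Power = Φ( δ / (σ√(1/n₁ + 1/n₂)) − z₁₋α/₂ )

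= Φ( 0.5 / √(2/96) − 2.387 ) = Φ(3.464 − 2.387) = Φ(1.077) = 85.9%.

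The t version gives 85.4%. Both are within two points of the stated 84%, so the plan's figure is not in dispute.

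**5. What lost pairs would cost (illustration only).** Assume that a share f of CDE-UNMH supports give no rating, that their patients drop from a complete-case A1c analysis, and that One Hope keeps all 96. The documents give no value for f and do not prescribe complete-case analysis. The same formula with n₂ = 96(1 − f) gives:

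| f | CDE-UNMH n | Power |
|---|---|---|
| 0 | 96 | 85.9% |
| 10% | 86.4 | 83.8% |
| 25% | 72 | 79.4% |
| 50% | 48 | 67.1% |

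A small share hardly matters; a large one would. The table does not cover the other route to harm, in which supports without contact answer anyway and their guesses enter the model as ratings.

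**The case against.** The strongest reply is that the site contrast comes from silence. Section 2.2 sketches CDE-UNMH briefly and does not exclude supports, and Section 9.2 treats inclusion of supports as something to be found out. This stands. A reader might infer that CDE-UNMH support ratings often have no experience behind them, or that One Hope ratings all come from supports who took part. The documents support neither: they give no frequency, and the entry rule for supports is the same at both sites.

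On the models, a reader might infer that blanks will selectively remove CDE-UNMH patients. That is not established. Section 13.3 says multiple imputation may be used. The A1c model is longitudinal, and Section 11.1 does not say whether CAHPS-CC enters as a time-varying or a summary score, so one rating at any visit might keep a pair in. But imputation is only permitted, and an imputed rating for someone who never met the program has no clear meaning. The handling of unrated supports still needs stating.

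Two further inferences go too far. The no-shows in the Section 9.2 inventory are program-level data and are not shown to be enrolled patients. The survey's questions on physician bias might seem to misfit a program led by educators, but the items may be modified (Section 9.2) and the revised instrument is an attachment not available here. That attachment could also hold a skip rule.

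Finally, Aim 1 also draws on inventories, interviews and focus groups, and less involvement of supports may be a real program difference. Both are true, and both are reasons to measure contact directly.

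**Conclusion.** The point holds in a limited form. On the visible text, the plan breaks its own condition for a valid CAHPS-CC rating by asking every support without establishing contact, and it has no means of separating informed ratings from others. This applies at both sites and is possibly more frequent at CDE-UNMH. Up to 360 support ratings per site are exposed to the problem; the number actually affected is unknown.

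The consequences are the reading of support ratings under Aim 1 and the A1c, BMI and PHQ-9 analyses, which are secondary. The covariates that Section 11.2 lists for its change-score regressions include participants' CAHPS-CC but not the supports' CAHPS-CC, so no effect on the primary outcomes is shown. Whether the secondary analyses would be distorted or reduced depends on how contact differs by site and how missing ratings are handled, and the documents settle neither. The conclusion assumes that the attached instrument contains no contact screen. The change is worth making because it is cheap and removes the uncertainty.

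**What to change.** 1. At 3, 6 and 12 months, add one item before CAHPS-CC, for patients and supports, recording whether the respondent has had direct contact with the named program.
2. Use a support's CAHPS-CC score as a program rating only where contact is reported. Flag the others and keep them apart.
3. Report the percentage of respondents with contact, by site and visit, as an Aim 1 result.
4. Keep all enrolled patients in the main Aim 1 patient comparison, and present the comparison limited to those with contact as a sensitivity analysis. Restricting the main comparison would select on engagement after enrolment, which the programs may themselves influence.
5. Do not require the support's CAHPS-CC score as a covariate in the main A1c, BMI and PHQ-9 models. It is collected only after baseline, so it cannot serve as a baseline adjustment. If it is kept in a supplementary model, state its form and how unrated supports are handled.

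The cost is one survey item, some wording in Sections 9.2 and 11.1, and fewer usable support ratings.

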Note: It is coincidental that the power (and effect sizes) are the same for each of the three secondary outcomes

11.3 Describe the steps that will be taken to secure the data (e.g., training, authorization of access, password protection, encryption, physical controls, certificates of confidentiality, and separation of identifiers and data) during storage, use, and transmission.

Training Requirement for Members of the Research Team: All members of the Research Team will receive training in research on human subjects. Each will take the online Human Subjects Research Training Modules from the Collaborative Institutional Training Initiative (CITI) which fulfill the requirement for NIH human subjects training. They will also take a HIPAA compliance training. PDCSs will be trained in phlebotomy. The CTSC Clinical Research Laboratory's ASCP-certified Medical Laboratory Scientist will also provide additional Good Laboratory Training and Competency to assist with site-specific collection and quarterly technical competency testing through direct observations of the PDCS phlebotomists at each site. A certified phlebotomist at One Hope, will be available to provide technical assistance to the PDCSs in an ongoing way. All Data Collectors will also receive a 2-day Mental First Aid training (Training was conducted in Spanish in April 2017 by a certified trainer).

Certificate of Confidentiality: We have obtained a Certificate of Confidentiality (CoC) from the National Institutes of Health (NIH). CoC's are issued by NIH to protect the privacy of research subjects by protecting investigators and institutions from being compelled

PROTOCOL TITLE: Comparing Program Options for Latinos with Diabetes

to release information that could be used to identify subjects with a research project. The process for obtaining a CoC is that we must first obtain approval from the UNM HSC HRPO and then we submit the approved consent form to NIH for their approval. We obtained our approved CoC on December 1, 2016 (see attachment).

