Research Team Expertise. **[name] (the PI) and [name] (the Co-PI)** have a close partnership and have assembled a seasoned multi-disciplinary team at UNM that includes collaboration with the two sites. The investigators have extensive experience working on issues of health disparity and demonstrated ability to conduct research in Spanish-speaking contexts, including with the population of study. The diverse composition of the Research Team will create a powerful, complementary blend of patient-engagement, knowledge, and experience; academic and medical knowledge; and research acumen. This synergistic skill set will make this unique project successful.

Describe other resources available to conduct the research: For example, as appropriate:

1. *Justify the feasibility of recruiting the required number of suitable subjects within the agreed recruitment period. For example, how many potential subjects do you have access to? What percentage of those potential subjects do you need to recruit?*

21.0

PROTOCOL TITLE: Comparing Program Options for Latinos with Diabetes

Our recruitment plan is feasible based on our previous experience. Below we provide a detailed presentation of our recruitment rate and plans for follow-up. We attempted to create a realistic recruitment plan that would fit seamlessly with the work required for all parts of the study. Below is the recruitment detail:

Year	Month	total	Baseline # participants recruited and appointments each month	3 months # of appointm ents each month	6 months # of appointm ents each month	12 month # of appointm ents each month	Total # of appoint ments each month	Total Appoint ments for each data collector each month
2017	Jan							
	Feb		32				32	8
	Mar	64	32				32	8
	Apr	96	32				32	16
	May	128	32	32			64	16
			25% achieved					
	Jun	160	32	32			64	16
	Jul	192	32	32			96	24
	Aug	224	32	32	32		64	24
	Sept	256	32	32	32		96	24
			50% achieved 25% required					
	Oct	288	32	32	32		96	24
	Nov	320	32	32	32		96	24
	Dec	352	32	32	32		96	24
2018	Jan	384	32	32	32	32	128	32
			75% achieved 50% required					
	Feb	416	32	32	32	32	128	32
	Mar	448	32	32	32	32	128	32
	Apr	480	32	32	32	32	128	32
			100% achieved					
	May			32	32	32	96	24
	Jun		75% required	32	32	32	96	24
	Jul			32	32	32	96	24
	Aug				32	32	64	16
	Sept		100% required		32	32	64	16

PROTOCOL TITLE: Comparing Program Options for Latinos with Diabetes

	Oct				32	32	64	16
	Nov				32	32	8	
	Dec				32	32	8	
2019	Jan				32	32	8	
	Feb				32	32	8	
	Mar				32	32	8	

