24.0 Local Number of Subjects

24.1 *Indicate the total number of subjects to be accrued locally.*

Local Comparator Sites: We will compare 2 diabetes self-management program models used by many Latino patients from low-income households in Albuquerque, New Mexico: 1) The Diabetes Self-Management Support Empowerment Model at the University of New Mexico Hospital and 2) The Chronic Care Model at One Hope Centro de Vida Health Center.

Subjects: We will recruit a total of 240 patient-social support pairs from the two program sites: patients (N=240: 120 at each site) and a corresponding social support of each enrolled patient (N=240 – 120 at each site). We will also recruit up to 6 staff and providers from each site each year to participate in interviews.

In addition, we will recruit the seven members of our Patient Advisory Board.

24.2 If applicable, distinguish between the number of subjects who are expected to be enrolled and screened, and the number of subjects needed to complete the research procedures (i.e., numbers of subjects excluding screen failures.)

Our experience with successful recruitment leads us to believe that we will be successful enrolling according to the plan we have laid out. Based on our experience working with this population in Albuquerque, our retention rates average 80-85%, which are consistent with other studies involving a similar population. To assure a conservative estimate, we estimated an attrition rate of 20% in our target recruitment.

Our previous study experience has demonstrated that we have the capacity to retain participants. We would like to emphasize our expertise and skill working with this patient population. The PI and the Co-PI have a strong record of working closely with individuals in the community and we have a cultural, linguistic and intellectual understanding of things that are important to patients and how to engage them. This makes a huge difference in the way that we, as researchers, interact with patient participants. Moreover, our PDCSs at both sites will be members of the patient population—Latino diabetes patients from low-income households. We believe that this will make a significant difference in the way that participants respond to and interact with our research project. These factors will assist us in retaining participants.

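### The four data collectors appear to be assigned by site, with no rotation, recorded collector ID or interviewer term, so interviewer effects on the orally given measures could not be separated from the program effect.

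*Combined protocol and SAP*

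**What the plan says.** **Who collects.** Section 9.2 (Surveys) states: "We will hire four individuals from the population of study to work as PDCSs". It then says "The PDCS at each site will administer a survey orally to all patient and social support participants at baseline", with follow-up at 3, 6 and 12 months. Section 11.5 repeats the site-based wording: "The PDCS at each site will administer a survey to all patient and social support participants". The survey contains the DKQ and PAM-13 (the co-primary outcomes), the PHQ-9 (a secondary outcome) and, after baseline only, the CAHPS-CC.

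**Site assignment.** Two other places can be read as site-based. Section 11.3 mentions "quarterly technical competency testing through direct observations of the PDCS phlebotomists at each site", and section 24.2 says "our PDCSs at both sites will be members of the patient population". The recruitment table before section 22.0 has a column for "Total Appoint ments for each data collector each month", which divides all appointments over four people (32/4 = 8 a month) without splitting them by site. No section says that a PDCS works at only one site, and none says that PDCSs rotate.

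**Control of interviewing.** Section 17.1 says PDCSs will learn to conduct surveys. Section 11.4 gives one coordinator daily oversight of schedule and protocol. The only direct observation of technique is for phlebotomy. Section 25.2 asks PDCSs to build rapport. Nothing is said about recording who did a visit, keeping the same PDCS for a participant, or blinding PDCSs to the hypothesis in section 11.2 that favors the Chronic Care Model program.

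**Analysis.** The propensity score and the mixed model in section 11.1, and the regression behind the power figures in section 11.2, have no interviewer term.

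**The concern.** Reading knowledge, activation, depression and cultural-competence items aloud leaves room for interviewers to differ in pace, prompting and rapport. If two small teams each serve one program, a difference between the teams looks exactly like a difference between the programs. Recruiting more patients per interviewer does not remove it, because the number of interviewers stays the same.

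Both co-primary outcomes are exposed. So is CAHPS-CC, which asks about bias, discrimination and trust, and which also enters the A1c mixed model and the power regression as a covariate. A team-level shift in CAHPS-CC could therefore move the adjusted site estimates for other outcomes as well. Unlike the other differences between two single-site programs, this one can be avoided by scheduling.

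**Working it through.** **1. Inputs from section 11.2.** 120 patients per site with 20% attrition gives 120 × 0.80 = 96 completers per site. DKQ: difference 2.2, SD 3.8, stated power 96% at α = 0.025. PAM-13: difference 12.7, SD 24.8.

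**2. The plan's own figure.** SE = 3.8 × √(2/96) = 0.548. 2.2/0.548 = 4.01. Power = Φ(4.01 − 2.241) = 96.2%, so the stated 96% for DKQ reproduces. This calculation treats all 96 patients per site as independent, with no interviewer component.

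**3. Assumptions not in the documents.** Two PDCSs per site, each working at that site only, with 96/2 = 48 completers each. Interviewer ICC of the analysed score (for DKQ and PAM-13, the change score): 0 to 0.05.

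**4. Effect of ignoring interviewer.** The variance of the site contrast is multiplied by DEFF = 1 + (48 − 1) × ICC. Actual two-sided error of a nominal 0.025 test = 2 × [1 − Φ(2.241/√DEFF)]. DKQ power, with the added variance allowed for and a normal critical value, = Φ(4.01/√DEFF − 2.241).

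| ICC of analysed score | DEFF | Actual error | DKQ power |
|---|---|---|---|
| 0 | 1.00 | 2.5% | 96% |
| 0.01 | 1.47 | 6.5% | 86% |
| 0.02 | 1.94 | 10.8% | 74% |
| 0.05 | 3.35 | 22% | 48% |

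The SD of the between-site shift caused by interviewers is √(2 × ICC × SD²/2) = SD × √ICC. At ICC 0.05 this is 0.85 DKQ points (39% of 2.2) and 5.5 PAM-13 points (44% of 12.7). Section 11.2 also gives α = 0.0125. At that level (critical value 2.498), ICC 0.01 raises the error to about 3.9%.

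**5. What cancels in a change score.** Let b_k be the stable effect of interviewer k, and p_k0 and p_k6 that interviewer's shares of the site's baseline and 6-month visits. The contribution to the site's mean change is Σ(p_k6 − p_k0) × b_k. It is zero when the shares are equal at the two visits, even if individual participants change interviewer. A simulation with two nested PDCSs per site, 96 completers per site, visit correlation 0.5 (assumed) and raw-score ICC of 0.005, 0.02 or 0.05 gave actual error of 2.3% to 2.6% against a nominal 2.5%. That held both with the same PDCS at both visits and with random switching. The larger values in the table therefore need interviewer effects that survive differencing: drift, turnover or changing shares, or effects that differ by visit or program.

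**6. What does not cancel.** Sections 9.2 and 11.5 say CAHPS-CC is not given at baseline, so nothing is subtracted.

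**7. Can the analysis repair it later?** Under strict nesting, the site indicator is the sum of that site's PDCS indicators, so site and a fixed PDCS factor cannot both be estimated. Treating four PDCSs as random leaves 2 degrees of freedom for the site test. The critical value is then 6.21, and DKQ power is about 35% even at ICC 0. If each PDCS does about half of their visits at each site, PDCS main effects balance out of the site contrast and the factor costs 3 degrees of freedom.

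**The case against.** The strongest reply has four parts.

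- **Assignment.** A reader might infer that interviewer and program are fully confounded. The documents do not go that far: exclusive site assignment is the natural reading of sections 9.2 and 11.5 but is never stated. The phrase in section 24.2 fits shared staff too, and the workload table pools all four PDCSs. This stands, so the point has to be conditional.
- **Change scores.** A reader might also infer that interviewer effects cancel only if one person does both of a participant's visits. Steps 5 and 6 show otherwise. Steady shares are enough for stable effects, so the exposure of DKQ, PAM-13 and PHQ-9 is much narrower than their oral administration suggests. This also stands.
- **Other measures.** A1c is a laboratory assay. BMI uses a standardized protocol, calibrated scales and averaged duplicate readings, so it is only weakly exposed. CAHPS-CC, where nothing cancels, is neither a primary nor a secondary outcome. All true, although CAHPS-CC is the Aim 1 survey measure and a model covariate.
- **Design.** Each program has one site, so staff, facility and access are already inseparable from program, and rotation removes only one component. That is correct, but this component is the one that scheduling can remove.

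A further inference, that a PDCS might rate a program they attend, has no support. Section 24.2 describes the PDCSs as members of the patient population, not as patients of either program.

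**Conclusion.** The point holds conditionally. If the wording in sections 9.2 and 11.5 means what it appears to mean, interviewer effects on DKQ, PAM-13, PHQ-9 and CAHPS-CC cannot be separated from the program effect, and nothing in the plan would detect or bound them.

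The size is unknown. The range of 2.5% to 22% actual error is an illustration that rests on an assumed ICC of the analysed score between 0 and 0.05, two PDCSs per site and equal loads. For change scores with steady interviewer shares, the true figure could be close to the nominal 2.5%. The exposure is clearest for CAHPS-CC. The change is worth making because it is cheap, has to be in place before data are collected, and cannot be replaced by later analysis if collection is strictly nested.

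**What to change.** In sections 9.2 and 11.5:

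- State that all four PDCSs work at both sites on a rotating roster, each doing about half of their appointments at each site.
- Keep the same PDCS for a participant's baseline and 6-month visits where possible.
- Store the PDCS ID with every visit in REDCap.

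In section 11.1, include PDCS as a factor in the site models, at least as a sensitivity analysis.

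This needs no added staff or visits, only one REDCap field. Both programs are in Albuquerque, all PDCSs are fluent in Spanish, one coordinator supervises them, and section 19.1 already allows appointments at a location that suits the participant. The cost is some travel within the city and less scheduling flexibility. Rotation and same-PDCS follow-up will sometimes conflict, which is why the second is asked for only where possible.
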